7.1.2. Liver chemistry stopping criteria

Study treatment or Investigational Product must stop immediately when participant meets one of the criteria described in Table below:

Table 3 Liver Chemistry Stopping Criteria - Liver Stopping Event for phase III - IV studies

Liver Chemistry Stopping Criteria - Liver Stopping Event	
If Baseline ALT ≤ 1.5x ULN	
ALT-absolute	ALT ≥ 8xULN
ALT Increase	ALT ≥ 5xULN but <8xULN persists for ≥2 weeks (with bilirubin <2xULN and no signs or symptoms of acute hepatitis or hypersensitivity)
Bilirubin^{1,2}	ALT ≥ 3xULN and bilirubin ≥ 2xULN (>35% direct bilirubin)
Cannot Monitor	ALT ≥ 5xULN but <8xULN and cannot be monitored every 1 - 2 weeks
Symptomatic³	ALT ≥ 3xULN with symptoms (new or worsening) believed to be related to liver injury or hypersensitivity
If Baseline ALT > 1.5x ULN	
ALT-absolute	ALT ≥ 5x baseline OR > 500 U/L (whichever occurs first)
ALT Increase	ALT ≥ 3x baseline but <5x baseline persists for ≥2 weeks (with bilirubin <2xULN and no signs or symptoms of acute hepatitis or hypersensitivity)
Bilirubin^{1,2}	ALT ≥ 3x baseline OR > 300 U/L (whichever occurs first) and bilirubin ≥ 2xULN
Cannot Monitor	ALT ≥ 3x baseline but <5x baseline and cannot be monitored every 1 - 2 weeks
Symptomatic³	ALT ≥ 3x baseline and symptoms (new or worsening) believed to be related to liver injury or hypersensitivity.

1. Serum bilirubin fractionation should be performed if testing is available. If serum bilirubin fractionation is not immediately available, discontinue study intervention for that participant if ALT ≥3xULN **and** bilirubin ≥2xULN. Additionally, if serum bilirubin fractionation testing is unavailable, **record presence of detectable urinary bilirubin on dipstick**, indicating direct bilirubin elevations and suggesting liver injury.
2. All events of ALT >3xULN and bilirubin >2xULN (>35% direct bilirubin) must be reported as an SAE (excluding studies of hepatic impairment or cirrhosis); INR measurement is not required, and the threshold value stated will not apply to participants receiving anticoagulants.
3. New or worsening symptoms believed to be related to liver injury (such as fatigue, nausea, vomiting, right upper quadrant pain or tenderness, or jaundice) or believed to be related to hypersensitivity (such as fever, rash or eosinophilia).

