7.1.1. Liver monitoring event – Increased monitoring

A liver monitoring event is an occurrence of predefined liver chemistry changes that triggers increased monitoring of the participant's liver chemistries, but no action is taken with study treatment unless liver chemistry stopping criteria are met.

Liver monitoring event criteria:

- Baseline ALT $\leq 1.5x$ ULN: ALT $\geq 5x$ ULN and $< 8x$ ULN and bilirubin $< 2x$ ULN without symptoms believed to be related to liver injury or hypersensitivity.
- Baseline ALT $> 1.5x$ ULN: ALT $\geq 3x$ baseline and $< 5x$ baseline and bilirubin $< 2x$ ULN without symptoms believed to be related to liver injury or hypersensitivity

Actions:

- Notify the VH medical monitor within 24 hours of learning of the abnormality to discuss participant safety.
- Participant can continue study intervention
- Participant must return every 2 weeks for repeat liver chemistries (ALT, AST, alkaline phosphatase, bilirubin) until resolution or stabilisation (ALT $< 5 \times$ ULN on 2 consecutive evaluations)
- If at any time participant meets the liver chemistry stopping criteria, proceed as described below

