- Examples of such events include invasive or malignant cancers, intensive treatment in an emergency room or at home for allergic bronchospasm, blood dyscrasias or convulsions that do not result in hospitalization, or development of drug dependency or drug abuse.

Is associated with liver injury and impaired liver function defined as:

- ALT \geq 3xULN and total bilirubin* \geq 2xULN (>35% direct), **or**
- ALT \geq 3xULN and INR** $>$ 1.5.

* Serum bilirubin fractionation should be performed if testing is available; if unavailable, measure urinary bilirubin via dipstick. If fractionation is unavailable and ALT \geq 3xULN and total bilirubin \geq 2xULN, then the event is still to be reported as an SAE.

** INR testing not required per protocol and the threshold value does not apply to participants receiving anticoagulants. If INR measurement is obtained, the value is to be recorded on the SAE form.

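### Table 3, baseline ALT above 1.5xULN: footnote 1 stops drug at ALT 3xULN, while the Bilirubin row it is attached to needs ALT 3x baseline or above 300 U/L

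*Protocol*

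**What the plan says.** Protocol Section 7.1.2 introduces Table 3 as mandatory: "Study treatment or Investigational Product must stop immediately when participant meets one of the criteria described in Table below". The table has two blocks, split at a baseline ALT of 1.5xULN, and each has a Bilirubin row carrying footnote markers 1 and 2.

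- **Lower block (baseline ALT up to 1.5xULN).** The row needs ALT of at least 3xULN, bilirubin of at least 2xULN, and more than 35% direct bilirubin.
- **Upper block ("If Baseline ALT > 1.5x ULN").** The row reads "ALT ≥ 3x baseline OR > 300 U/L (whichever occurs first) and bilirubin ≥ 2xULN". It sets no condition on the direct fraction.
- **Footnote 1, marked on both rows.** "If serum bilirubin fractionation is not immediately available, discontinue study intervention for that participant if ALT ≥3xULN", together with bilirubin of at least 2xULN. It has no baseline qualifier.

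Nothing elsewhere in the protocol confines footnote 1 to the lower block or restates it on the baseline scale.

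**The concern.** In the lower block the footnote fits its row. The row depends on the direct fraction, and the footnote says what to do when that fraction cannot be had at once, keeping the same ALT threshold.

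In the upper block it does not fit. The row does not use the direct fraction, so whether fractionation is available should not affect the decision. The footnote nevertheless makes it do so, and it replaces a baseline-scaled ALT threshold with a lower ULN-scaled one. While the fraction is pending or unobtainable, the footnote requires a stop. On the row alone, no stop is required, whatever the fraction turns out to be.

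This is the combined ALT-bilirubin criterion, and a stop under Section 7.1.2.1 is not trivial: no further injection may be given until the sponsor's safety committee approves. Sites need a single reading of it.

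**Working it through.** **Inputs from the protocol**
- Upper-block row: ALT ≥3 x baseline, or ALT >300 U/L, with bilirubin ≥2xULN (Table 3).
- Footnote 1: ALT ≥3 x ULN with bilirubin ≥2xULN, fraction not at hand (Table 3).
- Eligible baselines: exclusion 31 removes screening ALT of 3xULN or more, so 1.5 to 3xULN is enrollable. In Germany (Section 10.12.4) the cap is 5xULN, or 3xULN if bilirubin is at least 1.5xULN with more than 35% direct.

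**Assumption.** The protocol gives no ULN in U/L. I use 40 U/L for the example and 30 to 60 U/L as a range.

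**Where the rules part.** Write baseline ALT as b x ULN, with b > 1.5. Then 3 x baseline = 3b x ULN, which exceeds 4.5 x ULN, so the footnote threshold of 3 x ULN is lower unless the 300 U/L alternative applies first. With bilirubin ≥2xULN, the footnote is met and the row is not when

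3 x ULN ≤ ALT, and ALT < 3 x baseline, and ALT ≤ 300 U/L.

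Above that band both texts stop drug. Below it neither does.

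| ULN (assumed) | Baseline | Footnote: 3 x ULN | Row: 3 x baseline | Band of disagreement (U/L) |
|---|---|---|---|---|
| 30 | 60 (2xULN) | 90 | 180 | 90 to <180 |
| 40 | 80 (2xULN) | 120 | 240 | 120 to <240 |
| 40 | 100 (2.5xULN) | 120 | 300 | 120 to <300 |
| 50 | 100 (2xULN) | 150 | 300 | 150 to <300 |
| 60 | 120 (2xULN) | 180 | 360 (300 applies first) | 180 to 300 |

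Just above the block boundary (b = 1.51) the band is narrower. At ULN 40 it runs from 120 to 3 x 60.4 = 181.2 U/L. It becomes essentially empty only if ULN reaches 100 U/L, where 3 x ULN = 300 U/L.

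**Worked case.** ULN 40, baseline 80, on-study ALT 160 U/L, bilirubin 2.5xULN, no symptoms.
- Bilirubin row: 160 < 240 and 160 ≤ 300, so not met.
- ALT-absolute row: 160 < 5 x 80 = 400 and 160 ≤ 500, so not met.
- ALT-increase, cannot-monitor and symptomatic rows: each needs at least 3 x baseline = 240, so not met.
- Section 7.1.1 monitoring event: needs ALT of at least 3x baseline and bilirubin below 2xULN, so not met.
- Footnote 1: 160 ≥ 120 and bilirubin ≥2xULN, so discontinue if the fraction is not at hand.

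**German cap.** A participant with baseline ALT of 3 to <5xULN meets the footnote's ALT limb before any rise in ALT. At ULN 40 and baseline 160 U/L, 3 x baseline is 480, so 300 U/L applies first and the band is 120 to 300 U/L.

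**The case against.** The strongest reply is that the footnote will seldom operate. Section 8.2.2 sends protocol laboratory tests to the central laboratory, and note a to Table 4 has direct bilirubin run automatically whenever total bilirubin exceeds 1.5xULN. Every case in the band has bilirubin of at least 2xULN, so the fraction will normally arrive. What remains is the wait for it, and local-laboratory results, which Section 10.11.1 allows for safety decisions during COVID-19 disruption. With injections two months apart, a short wait will rarely decide an injection. It matters more for daily oral dosing. The affected group is also likely to be small: cirrhosis and moderate to severe hepatic impairment are excluded, and Section 4.1.2 requires any Grade 1 or higher ALT at screening or Day 1 to be discussed with the Medical Monitor before long-acting dosing. All of this stands and limits the reach. It does not say which text governs when the footnote does operate.

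It can also be argued that footnote 1 was meant only for the lower block, the only one whose row uses the direct fraction. That is plausible, but the marker sits on both rows and the wording sets no limit.

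Two stronger readings are tempting, and the protocol does not support them.

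- **That a participant who misses the row simply continues on drug.** Section 8.3.10.2 requires Medical Monitor consultation at ALT of 3xULN or more before CAB LA + RPV LA is started or continued. Section 2.3.1 has CAB withdrawn where drug-induced liver injury is suspected without a compelling alternative cause. Section 8.3.4 requires 24-hour reporting of the combined event when more than 35% of bilirubin is direct. Section 8.3.10.3 may also lead to withholding. None of these is the footnote's mandatory stop, and the Section 8.3.10.2 rule is written for the injectable regimen, not BIK. Together, though, they rule out describing the outcome as unrestricted continuation.
- **That Table 3 contradicts the SAE definition in Section 10.2.2**, because a combined event reportable on the ULN scale can fall outside the baseline-scaled row. Section 10.2.2 sets what is reported; Table 3 sets when drug stops. Nothing in the protocol says every liver SAE must be a stopping event, so different thresholds are not in themselves an error.

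**Conclusion.** The inconsistency is real and lies within one table. For baseline ALT above 1.5xULN with bilirubin of at least 2xULN, the row and its own footnote disagree for ALT from 3xULN up to the lower of 3x baseline and 300 U/L. On the assumed ULN of 40 U/L, that is 120 to 239 U/L at baseline 80 and 120 to 299 U/L at baseline 100. A band exists across the assumed ULN range of 30 to 60 U/L. Its existence follows from the text whenever ULN is below 100 U/L; only the U/L figures depend on the assumption.

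How many participants would fall in the band cannot be derived from the protocol. It is probably few, given reflex fractionation and the eligibility limits. The point is still worth correcting because it changes the threshold of a mandatory stopping rule. No view is taken here on which threshold is right.

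**What to change.** Reconcile footnote 1 with the Bilirubin row of the baseline ALT >1.5xULN block. State whether the footnote applies to that block at all, given that its row does not use the direct fraction. If it does apply, state on which ALT scale, and what follows once the fraction becomes known. If it does not, remove the marker from that row. The clinical team chooses the threshold.

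The cost is one footnote edit in the next amendment and a short memo to sites. Data collection and the statistical analysis are unaffected.

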7.1.2.1. Liver Chemistry Stopping Criteria, Participant Management and Follow-Up

Participants who develop ALT $\geq 5 \times$ ULN must be followed weekly until resolution or stabilization (ALT $< 5 \times$ ULN on 2 consecutive evaluations).

When any of the liver chemistry stopping criteria is met, do the following:

- Immediately hold IP. If on LA therapy, **do not** administer another injection until approval is received from the ViiV Safety and Labelling Committee.
- Report the event to the Medical Monitor within 24 hours of learning its occurrence.
- Complete the liver event eCRF and SAE eCRF, where applicable.
- Complete the liver imaging and/or liver biopsy eCRFs if these tests are performed.
- Perform liver event follow up assessments (described below), and monitor the participant until liver chemistries resolve, stabilize, or return to Baseline values as described below.
- Make every reasonable attempt to have participants return to clinic within 24 hours for repeat liver chemistries, liver event follow-up assessments (see below), and close monitoring.
- A specialist or hepatology consultation is recommended.
- Monitor participants twice weekly until liver chemistries (ALT, AST, alkaline phosphatase, bilirubin) resolve, stabilize or return to within Baseline values.

Make every attempt to carry out the **liver event follow-up assessments** described below:

- Viral hepatitis serology including:
 - Hepatitis A immunoglobulin M (IgM) antibody;
 - Hepatitis B surface antigen (HBsAg) and Hepatitis B Core Antibody (IgM);
 - Hepatitis C RNA;
 - Hepatitis E IgM antibody;
 - Cytomegalovirus IgM antibody;
 - Epstein-Barr viral capsid antigen IgM antibody (or if unavailable, obtain heterophile antibody or monospot testing);
- Syphilis screening;
- Drugs of abuse screen including alcohol;
- Serum acetaminophen test (N-acetyl-para-aminophenol [APAP] adduct test). The site must contact GSK when this test is required. Please refer to the central laboratory manual.

- Blood sample for pharmacokinetic (PK) analysis, obtained during follow up assessments. Record the date/time of the PK blood sample draw and the date/time of the last dose of investigational product prior to blood sample draw on the eCRF. If the date or time of the last dose is unclear, provide the participant's best approximation. If the date/time of the last dose cannot be approximated OR a PK sample cannot be collected in the time period indicated above, do not obtain a PK sample. Instructions for sample handling and shipping are in the SPM.
- Serum creatine phosphokinase (CPK) and lactate dehydrogenase (LDH);
- Fractionated bilirubin, if total bilirubin is greater than 1.5xULN;
- Obtain complete blood count with differential to assess eosinophilia;
- Anti-nuclear antibody, anti-smooth muscle antibody, and Type 1 anti-liver kidney microsomal antibodies, and quantitative total immunoglobulin G (IgG or gamma globulins);
- Liver imaging (ultrasound, magnetic resonance, or computerized tomography) and/or liver biopsy to evaluate liver disease; complete Liver Imaging and/or Liver Biopsy CRF forms.
- Record the appearance or worsening of clinical symptoms of hepatitis, or hypersensitivity, fatigue, decreased appetite, nausea, vomiting, abdominal pain, jaundice, fever, or rash as relevant on the AE report form;
- Record use of concomitant medications, acetaminophen, herbal remedies, other over the counter medications, or putative hepatotoxins, on the concomitant medications report form. Record alcohol use on the liver event alcohol intake case report form.

7.1.3. General Guidance on Restart

- The definition of restart is not always clear cut in medical practice. Restarts should be limited to cases in which there is clear evidence that the underlying cause of the liver event is not related to study drug.
- For long acting agents, a restart may actually be continuation of therapy rather than a true re-start due to the timeframe between dose administration relative to decision making on allowing a restart.
- If protocol defined stopping criteria for liver chemistry elevations are met (Section 7.1.2), study drug must be stopped. Participants who meet liver chemistry stopping criteria should not be retreated with investigational product unless an exemption has been approved by the VSLC. The guideline for Restart approved by the VSLC, which is maintained as a separate document must be followed.
- If the restart is approved by the VSLC in writing, the participant must be provided with a clear description of the possible benefits and risks of drug administration, including the possibility of recurrent, more severe liver injury or death.

- Ethics Committee or Institutional Review Board approval of drug restart must be obtained, as required.
- The participant must also provide signed informed consent specifically for the IP restart. Documentation of informed consent must be recorded in the study chart.
- Study drug must be administered at the dose specified by the VSLC.
- Participants approved by the VSLC for restart of IP must return to the clinic once a week for liver chemistry tests for a minimum of one month and thereafter for as long as clinically indicated and then laboratory monitoring may resume as per protocol. Longer durations of close monitoring may be required for long acting IP.

7.1.3.1. Drug Restart

“Drug restart” can be approved by the VSLC for **defined non-drug-induced** liver injury if no evidence of:

- immunoallergic injury /HLA association with injury
- alcoholic hepatitis

Study drug must be held while labs and evaluation are completed to assess diagnosis.

7.1.3.1.1. ***Drug Restart Following Transient Resolving Liver Events Not Related to IP***

Approval by the VSLC for drug restart or additional IM administration can be considered where:

- Abnormalities in liver chemistries have a clear underlying cause (e.g., biliary obstruction, hypotension, acute viral hepatitis, and liver chemistries have significantly improved).
- If definitive non-study drug related diagnosis, restart will be considered once ALT < 3x ULN (for participants with baseline ALT < 1.5x ULN) or < 3x baseline ALT value (for participants with baseline ALT > 1.5x ULN).
- Ethics Committee or Institutional Review Board approval of drug restart must be obtained, as required.
- If restart / redosing of drug is approved by the VSLC in writing, the participant must be provided with a clear description of the possible benefits and risks of drug administration, including the possibility of recurrent, more severe liver injury or death.
- The participant must also provide signed informed consent specifically for the restart. Documentation of informed consent must be recorded in the study chart.
- Study drug must be administered at the dose specified by the VSLC.

Participants approved by the VSLC for restarting or re-dosing IP must return to the clinic once a week for liver chemistry tests for a minimum of one month and thereafter for as long as clinically indicated and then laboratory monitoring may resume as per protocol. If protocol defined stopping criteria for liver chemistry elevations are met, study drug must be stopped.

7.1.4. QTc Stopping Criteria

A participant who has a QTc interval >550 msec considered causally related to IP will be withdrawn from the study. The QTc should be based on averaged QTc values of triplicate electrocardiograms obtained over a brief (e.g., 5 to 10 minute) recording period.

If an alternative cause of the QT prolongation is determined (e.g., participant receiving drug known to cause prolonged QT or TdP), the IP may be restarted (or continued) after consultation and agreement with the Medical Monitor. RPV and RPV LA should not be administered to patients who are receiving a drug known to be associated with TdP.

When performing ECGs, the *same* QT correction formula *must* be used for *each individual participant* to determine eligibility for, and discontinuation from, the study. This formula may not be changed or substituted once the participant has been enrolled.

For example, if a participant is eligible for the protocol based on QTcB, then QTcB must be used for discontinuation of this individual participant as well.

Once the QT correction formula has been chosen for a participant's eligibility, the *same formula* must continue to be used for that participant *for all QTc data being collected for data analysis*. Safety ECGs and other non-protocol specified ECGs are an exception.

7.1.5. Virologic Failure

Only plasma HIV-1 RNA values determined by the central laboratory will be used to assess virologic failure.

7.1.6. Definition of Protocol-Defined Confirmed Virologic Failure

For the purposes of clinical management in this study, CVF is defined as:

Rebound as indicated by two consecutive plasma HIV-1 RNA levels ≥ 200 c/mL (Day 1 values are not applicable) after prior suppression to < 200 c/mL.

7.1.7. Managing Virologic Failure

Following study entry, no changes, or intensification of ART will be permitted prior to protocol-defined virologic failure, outside of the planned protocol regimens. Only plasma HIV-1 RNA values determined by the central laboratory will be used to assess virologic failure. Baseline plasma HIV-1 RNA is the assessment completed on study Day 1. The definition of confirmed virologic failure does not apply to participants in the LTFU Phase. These participants will be followed for the emergence of viral resistance.

Inadequate adherence is a common cause for virologic failure and should be explored as a first step in the management of study participants (e.g., at the first indication of inadequate virologic response or rebound). Upon notification that a participant's HIV-1 RNA plasma level qualifies him/her as a suspected virologic failure, the Investigator should query the participant regarding intercurrent illness, recent immunization, or interruption of oral therapy.

7.1.7.1. HIV-1 RNA Blips

HIV-1 RNA “blips” are not usually associated with subsequent virologic failure [DHHS, 2019]. Although the implications of persistent HIV-1 RNA levels between the lower level of detection and <200 c/mL are unclear, the risk of emerging resistance is believed to be relatively low.

Participants with transient increases in HIV-1 RNA (‘blips’ HIV-1 RNA <200 c/mL) are not considered suspected virologic failures and do not require a change in therapy.

Participants who have a HIV-1 RNA ≥ 50 c/mL and <200 c/mL at the key analysis timepoints (Month 6 and 12 [OLI and BIK] and Months 5 and 11 [D2]) must return to the clinic as soon as possible (but no later than 4 weeks after the date of the Months 6 or 12 [OLI and BIK] and Months 5 or 11 [D2I] visits, respectively) for a repeat HIV-1 RNA test such that the result falls within the same analysis window.

In order to better characterize HIV-1 RNA ‘blips,’ if there is a known reason / explanation for the blip (e.g., immunization, allergies, etc.), the study team should be notified of the reason and case context.

If the Investigator has concerns regarding persistent low-level viremia (HIV-1 RNA ≥ 50 c/mL and <200 c/mL), the Medical Monitor should be contacted to discuss participant management. Following discussion with the Medical Monitor, additional viral load testing may be performed between visits to determine the appropriate participant disposition for the next scheduled visit.

7.1.7.2. Suspected Virologic Failure

Upon notification that a participant's HIV-1 RNA plasma level meets the definition of virologic failure, the Investigator should confirm the definition is met by initiating a repeat of the HIV-1 RNA assessment.

The following guidelines should be followed for scheduling confirmatory HIV-1 RNA testing in an effort to avoid false-positive results:

- Confirmatory testing should be scheduled within 2 to 4 weeks following resolution of any intercurrent illness, during which time the participant should receive full dose of all IP.
- Confirmatory testing should be scheduled at least 4 weeks following any immunization, during which time the participant should receive full dose of all IP.

- If therapy is interrupted* due to toxicity management, non-compliance, or other reasons, confirmatory testing should be scheduled 2 to 4 weeks following resumption of full dose of all IP.
- The participant should have received full dose of IP for at least 2 weeks at the time confirmatory plasma HIV-1 RNA testing is done.

*Note: treatment interruption guidelines above may not apply for participants on CAB LA + RPV LA treatment. The study team should be contacted to discuss any treatment interruptions for participants meeting the definition of virologic failure.

In addition, the Investigator should query the participant regarding intercurrent illness, recent immunization, or interruption of therapy.

Sites should contact the Medical Monitor to discuss individual participants, whenever necessary.

